The aim of this study is to assess the safety and efficacy of LY2951742 300 mg administered every 30 days for the prevention of chronic cluster headache.

Clinical Protocol Synopsis: Study I5Q-MC-CGAM

Name of Investigational Product: LY2951742	
Title of Study: A Phase 3 Randomized, Double-Blind, Placebo-Controlled Study of LY2951742 with a Long-Term Open-Label Extension in Patients with Chronic Cluster Headache	
Number of Planned Patients/Subjects: Entered: 231 Enrolled/Randomized: Planned 162 Completed (SP III): 146	Phase of Development: 3
Length of Study: 30 months	
Estimated first patient visit: Jun 2015 Estimated last patient visit: Dec 2017	
Primary Objectives: The primary objective is to assess the efficacy of LY2951742 300 mg administered every 30 days compared with placebo in reducing the frequency of weekly cluster headache attacks in patients with chronic cluster headache. The primary outcome measure is the weekly cluster headache attack frequency. The primary endpoint is the overall mean change from baseline in weekly cluster headache attack frequency during the 12-week double-blind treatment phase with LY2951742 compared with placebo. The baseline cluster headache attack frequency is based on the last 14 days in the eligibility report (pre-randomization diary phase).	
Gated Objectives: 
• To assess the efficacy of LY2951742 300 mg compared with placebo in the estimated mean proportion of patients with a 50% or greater reduction from baseline in the weekly frequency of cluster headache attacks during the 12-week double-blind treatment phase.• To assess the efficacy of LY2951742 300 mg compared with placebo in the proportion of patients meeting sustained response through Week 12. For this analysis, sustained response is defined as a 50% or greater reduction in the weekly cluster headache attack frequency from baseline to Weeks 3/4 and maintained at Weeks 5/6, Weeks 7/8, Weeks 9/10, and Weeks 11/12.	

Other secondary objectives:

- To assess whether LY2951742 300 mg is superior to placebo on the following:
 - mean change in the weekly cluster headache attack frequency from baseline to each 2-week interval through Week 12
 - the proportion of patients with a 50% or greater reduction in the weekly cluster headache attack frequency from baseline at each 2-week interval through Week 12

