6.2.2. Other Secondary Objectives

- To assess whether LY2951742 300 mg is superior to placebo on the following:
 - mean change in the weekly cluster headache attack frequency from baseline to each 2-week interval through Week 12
 - the proportion of patients with a 50% or greater reduction in the weekly cluster headache attack frequency from baseline at each 2-week interval through Week 12
 - the proportion of patients with a 30% or greater reduction in the weekly cluster headache attack frequency from baseline at each 2-week interval through Week 12
 - proportion of patients reporting a score of 1 (“very much better”) or 2 (“much better”) on the Patient Global Impression of Improvement (PGI-I) at Month 1, Month 2, and Month 3

- To compare LY2951742 300 mg with placebo on the following safety and tolerability measures:
 - spontaneously reported treatment-emergent adverse events (TEAEs)
 - serious adverse events
 - adverse events leading to discontinuation
 - suicidal ideation and behaviors assessed by solicited questioning using the Columbia-Suicide Severity Rating Scale (C-SSRS).
- To assess the development and consequences of anti-drug antibodies (ADA) to LY2951742 in patients exposed to LY2951742; to provide samples for subsequent evaluation of neutralizing ADA (NAb).
- To evaluate the pharmacokinetics of LY2951742.

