(Visits 4 and 7) with the patient approximately 1 week after the first two IP administration visits during SP III to collect spontaneously reported AEs. At Visit 5, the patient will come into the office for the collection of blood samples 2 weeks after the first dose. During SP III, the patient will continue to record his or her cluster headache attack information daily in the ePRO diary.

- For patients who discontinue early in SP III, they should enter SP V.
- For patients who complete SP III, SP IV is an optional 1-year exposure, open-label treatment phase which is described below.
- For patients who choose not to enter SP IV, they should enter SP V.

During SP IV, the unblinded site personnel will continue to prepare the IP for each patient. All patients who enter SP IV will receive open-label monthly injections of LY2951742. All study procedures at Visit 9 must be completed prior to patients receiving the first dose of LY2951742 in SP IV. Patients and investigators will remain blinded to the SP III treatment assignments during SP IV. Each dose of IP will be administered as 3 SC injections at office visits: Visits 9 and 11 through 21. Since placebo patients will be transitioning to LY2951742 at Visit 9, all patients should remain in the office for 30 minutes for observation after administration of IP. Also, during SP IV, some patients may transition to LY2951742 300 mg supplied in 3 prefilled syringes with each syringe containing 100 mg. These patients should remain in the office for 30 minutes for observation after the first prefilled syringe injection. All patients will continue to record his or her cluster headache attack information daily in the ePRO diary until Visit 11.

Study Phase V is a 16-week post-treatment phase for safety follow-up.

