5.2. Determination of Sample Size

The study is planned to have a minimum of approximately 162 patients randomized 1:1 to placebo or galcanezumab 300 mg with the opportunity to increase the final sample size at an interim analysis if indicated in order to maintain a well powered study. To preserve blinding, details of the sample size and power calculations are omitted from this SAP and are provided in a separate document to the Ethical Review Board (ERB).

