SP III/IV/V Combined (GMB-treated time + post treatment time)		2) patients who received placebo during SP III and entered the open-label phase with at least one galcanezumab injection.	

Abbreviations: ePRO = electronic patient reported outcome; GMB = galcanezumab; SP = study phase.

a Analyses in SP III and first 4 weeks of SP IV combined, will be conducted for ePRO data only.

Treatment effects will be evaluated based on a 2-sided significance level of 0.05 for all the other efficacy and safety analyses. Ninety-five percent (95%) CI for the difference in least-square means (LSMeans) between treatment groups will be presented. Adjustments for multiple comparisons for the analyses corresponding to the primary and gated secondary objectives are described in the sections on the primary and secondary efficacy analyses below. There will be no adjustments for multiplicity for analyses of other data.

A repeated measures analysis refers to a restricted maximum likelihood (REML)-based, mixed-effects repeated measures (MMRM) analysis using all the longitudinal observations at each postbaseline visit/week.

Categorical comparisons between treatment groups for safety measures will be performed using Fisher's exact tests, where appropriate.

Any change to the data analysis methods described in the protocol will require an amendment ONLY if it changes a principal feature of the protocol. Any other change to the data analysis methods described in the protocol, and the justification for making the changes, will be described in the SAP and/or in the clinical study report.

Additional exploratory analyses of the data will be conducted as deemed appropriate.

Statistical analysis of this study will be the responsibility of Eli Lilly and Company (Lilly) or designee. SAS®software will be used to perform most or all statistical analyses.

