5.5.1.6. Baseline and Postbaseline Definition

Table CGAM.5.3 describes the rules for determining the patient population and baseline and postbaseline observations for each study phase and type of analysis. When “last of Visit x-x” is used in the table, the last nonmissing observation obtained in the visit interval will be used.

Table CGAM.5.3. Patient Population with Baseline and Postbaseline Definitions by Study Phase and Type of Analysis

Study Phase / Analysis	Patient Population	Baseline Observation	Postbaseline Observation(s)
Study Phase III (Treatment Phase)			
Continuous secondary efficacy analyses (Repeated measures)	Patients in ITT population with a baseline and at least one postbaseline observation	Visit 3	All Visits 4–9
TEAEs	Safety population	All Visits 1–3 before dosing	Visit 3 after dosing – through Visit 9 before dosing if applicable
Serious Adverse Events, Discontinuations due to Adverse Events	Safety population	NA	Visit 3 after dosing – through Visit 9 before dosing if applicable
C-SSRS categorical analyses	Patients in safety population with a baseline and at least one postbaseline C-SSRS assessment	Recent History: All Visits 1–3 excluding lifetime ^a All Prior History: Visits 1–3 including lifetime ^a	All Visits 3.01–9
Treatment-emergent abnormal laboratory values	Patients in safety population with normal laboratory values at all nonmissing baseline visits (with respect to direction being analyzed) and who have at least one postbaseline observation	All Visits 1–3	All Visits 3.01–9
Treatment-emergent immunogenicity	Patients in safety population who are evaluable for TE ADA	Visit 3	All Visits 3.01–9
Treatment-emergent changes in vital signs and weight, ECG parameters	Patients in safety population with a baseline and at least one postbaseline observation	Last non-missing value from Visits 1–3 for BP, pulse and ECG All Visits 1–3 for weight and temperature	All Visits 3.01–9
Continuous safety analysis of vital signs, weight, laboratory and ECG parameters (box-whisker plot)	Safety population	Last non-missing value from Visits 1–3	Visits 4–9

Patient Population with Baseline and Postbaseline Definitions by Study Phase and Type of Analysis

Study Phase / Analysis	Patient Population	Baseline Observation	Postbaseline Observation(s)
Study Phase III and IV combined (Double-blinded and open-label extension phase combined)			

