5.5.9. Safety Analyses

The safety analyses will be conducted on the safety population during the double-blind treatment phase (SP III), and on the GMB-treated population during the GMB-treated time (SP III/IV combined) and the GMB-treated time plus post-treatment time (SP III/IV/V combined). All the safety analyses outlined below will be conducted as long as the safety measures were collected at the specific study phase.

The safety and tolerability of treatment will be assessed by summarizing the following:

- adverse events
 - treatment-emergent adverse events
 - by PT
 - by PT nested within SOC
 - by maximum severity
 - serious adverse events by PT nested within SOC
 - adverse events leading to discontinuation by PT nested within SOC
 - adverse events of special interest
- suicide-related thoughts and behaviors by C-SSRS
- vital signs and weight
- laboratory measurements
- electrocardiograms
- antibodies (ADA and NAb)

The baseline and postbaseline for all safety measures are described in [Table CGAM.5.3](#) unless specified otherwise. For SAEs, only events with a start date during the post-baseline phase will be accounted for the corresponding study phase analysis.

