5.5.9.1. Categorical Safety Variables

Unless specified otherwise, the categorical safety analyses will include both scheduled and unscheduled visits.

Comparisons between treatment groups for all categorical safety measures will be made using Fisher's exact test for SP III in the safety population. Descriptive statistics only will be presented for the analyses with the GMB-treated population.

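### Adverse events that begin or worsen after an early exit from SP III appear to fall outside the only drug-versus-placebo safety comparison, and SP V events of placebo patients never given galcanezumab have no planned summary in SAP 5.5.9

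*SAP*

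**What the plan says.** Protocol 6.2.2 makes the safety comparison a secondary objective: "To compare LY2951742 300 mg with placebo on the following safety and tolerability measures", followed by TEAEs, SAEs and discontinuations due to adverse events among others. SAP 5.5.9.1 confines between-group testing to SP III in the safety population, by Fisher's exact test.

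SAP Table CGAM.5.3 gives one SP III post-baseline window for TEAEs, SAEs and discontinuations due to adverse events: "Visit 3 after dosing – through Visit 9 before dosing if applicable". For SAEs, SAP 5.5.9 adds a start-date rule: "For SAEs, only events with a start date during the post-baseline phase will be accounted for the corresponding study phase analysis". For TEAEs, SAP 5.5.9.1.1 judges emergence or worsening within the particular post-baseline period.

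Protocol 7.1 sends early stoppers out of that window: "For patients who discontinue early in SP III, they should enter SP V". Completers who decline the extension also go to SP V. SAP 5.5.5.1 ends a patient's SP III exposure at the SP III disposition date.

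The only adverse-event analysis in SAP 5.5.9 that reaches SP V is the combined SP III/IV/V summary of the GMB-treated population. Table CGAM.5.2 admits placebo patients to that population only once they have been injected with galcanezumab in SP IV. SAP 5.5.9.1 says of it: "Descriptive statistics only will be presented for the analyses with the GMB-treated population". According to the SAP revision history, the separate SP V safety analyses were taken out in Version 4.

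**The concern.** The length of time for which a patient contributes adverse events to the randomized comparison depends on whether the patient stays in SP III. Visit 9 is scheduled at Day 90, 30 days after the third dose, so a completer is counted for about 30 days after each of the three doses. A patient who leaves a few days after a dose appears to be counted only to the exit. Stopping happens after randomization and can be related to safety, so the two arms may be followed for different lengths of time for reasons linked to the outcome.

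Later events in galcanezumab stoppers are still summarized, but with no placebo column beside them. Later events in placebo patients who never switch are in no adverse-event summary in SAP 5.5.9. If a rare event tends to appear after stopping, the plan has no table that would show it by arm.

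**Working it through.** **1. How an event after exit is classified.** Take a constructed patient: second dose on Day 30, exit from SP III on Day 40, new event on Day 45.

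| Question | Source | Answer |
|---|---|---|
| Within 30 days of a dose and before Day 90? | Protocol Attachment 1 | Yes, 15 days after the dose |
| Within Visits 3 to 9 for this patient? | SAP Table CGAM.5.3; Protocol 7.1 | No, the patient is in SP V (Visits 23 and 24) |
| Does a rule return the event to SP III? | SAP 5.5.9 and Table CGAM.5.3 | None stated |
| Counted if on galcanezumab? | Tables CGAM.5.2 and 5.3 | Only in the descriptive SP III/IV/V summary |
| Counted if on placebo and never switched? | Table CGAM.5.2 | In no adverse-event summary in SAP 5.5.9 |

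The same event in a patient who stayed would enter the SP III comparison.

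**2. Number of early stoppers.** The protocol synopsis gives "Enrolled/Randomized: Planned 162 Completed (SP III): 146". The documents state no dropout rate, but 10% reproduces the figure: 162 × 0.90 = 145.8, or 146. Early stoppers: 162 − 146 = 16 (9.9%). Patients are "randomized 1:1 to placebo or galcanezumab 300 mg", so there are 81 per arm, and about 8 stoppers per arm if they split evenly.

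**3. Uncounted time.** Planned time to Visit 9 is 162 × 90 = 14,580 patient-days. Uncounted time is 16 × (90 − mean exit day). The exit day is an assumption.

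| Mean exit day | Uncounted patient-days | Share of 14,580 |
|---|---|---|
| 75 | 240 | 1.6% |
| 45 | 720 | 4.9% |
| 15 | 1,200 | 8.2% |
| 0 (ceiling) | 1,440 | 9.9% |

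**4. Average effect on incidence.** Assume a constant hazard, 10% stopping, and exit spread evenly over 90 days. If p is the true 90-day incidence, a stopper is counted with probability 1 − p / [−ln(1 − p)], and the counted incidence is 0.9p plus 0.1 times that probability.

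- p = 10%: 0.090 + 0.1 × 0.051 = 9.5%
- p = 20%: 0.180 + 0.1 × 0.104 = 19.0%
- p = 50%: 0.450 + 0.1 × 0.279 = 47.8%

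**5. Rare events clustering in one arm.** These are bounds, not predictions: two-sided Fisher's exact test with 81 per arm, all missed events in one arm. The SAP's criterion is "Treatment effects will be evaluated based on a 2-sided significance level of 0.05".

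- Counted 0 v 0 (p = 1.0); with six missed events, 6 v 0 (p = 0.028)
- Counted 8 v 4 (p = 0.37); with four missed events, 12 v 4 (p = 0.062)
- One missed event is 1/81 = 1.2 percentage points

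**6. Placebo time in SP V with no summary.** SP V lasts 112 days (16 weeks) or 120 days (two 60-day intervals). Eight placebo stoppers give 8 × 112 = 896 to 8 × 120 = 960 patient-days. If 10% of the 73 placebo completers decline SP IV (assumed), the group is 8 + 7.3 = 15.3 patients and 1,714 to 1,836 days. At 20% it is 22.6 patients and 2,531 to 2,712 days.

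**The case against.** The strongest reply is that an on-phase comparison is a legitimate choice. SP V is a post-treatment phase, and Protocol 8.4.3 requires a patient who needs a preventive that is not allowed to leave the study before it is started. Some events after exit will therefore follow a new treatment, and charging them to the randomized arm has its own cost. This stands, and it is why the present table should stay as it is.

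The exclusion is also an inference. No sentence says that early stoppers' events before Day 90 are dropped, and the early-termination visit is not mapped to a phase, so events up to that visit may count. This too stands, but it means that the assignment rule needs to be written down.

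A reader might infer that the events which caused stopping are lost. The documents do not support that. Such events normally start in SP III, count there as TEAEs if new or worsened, and have their own SP III row as discontinuations. How an event that becomes serious later is dated is not stated. The start-date sentence covers SAEs only, so for TEAEs the point rests on Table CGAM.5.3.

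A reader might also infer that all placebo patients' SP V events are lost. They are not: placebo patients who switched are counted to Visit 24.

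Other outputs soften the gap a little. The registry summary in SAP 5.9 tabulates SAEs by treatment group, without stating which phases it covers, and the DMC monitors safety. Neither is a prespecified comparison of events after exit.

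**Conclusion.** The point holds in a limited form. Adverse events that begin or worsen after an early exit appear to be outside the only drug-versus-placebo comparison, even within 30 days of a dose and within the same 12 weeks. SP V events of placebo patients who never received galcanezumab, whether early stoppers or completers who declined SP IV, have no adverse-event summary in SAP 5.5.9.

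The uncounted time is modest. It rests on the planned 16 stoppers and an assumed exit day, and the incidence figures also assume a constant hazard. The average effect on incidence is about half a point at a true 10% and one point at a true 20%. The case for action rests on rare events after stopping.

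It is tempting to say that the comparison is biased toward no difference, or that stoppers are the patients at highest risk. The documents give neither reasons for stopping by arm nor event rates in stoppers. If placebo patients stop more often, for example for lack of effect, the loss would fall more on placebo. The direction is unknown.

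**What to change.** - Keep the on-phase SP III table unchanged.
- Add a prespecified TEAE and SAE table by randomized arm for the safety population. Count from first dose to Visit 9 before open-label dosing or, for early stoppers, to Day 90, using events recorded at the early-termination and SP V visits.
- State in Table CGAM.5.3 how events at or after the early-termination visit, and in SP V, are assigned to a phase.
- Summarize SP V adverse events by SP III arm for patients who do not enter SP IV.

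The cost is SAP wording and date-based programming. No new collection is needed: Protocol Attachment 1 records adverse events at early termination and at Visits 23 and 24, and Protocol 10.2.1.1 collects SAEs to the last study visit. There are two drawbacks. Some added events will follow a change of treatment, and patients who refuse SP V, which Protocol 8.4.2 allows for, will have incomplete follow-up. Setting the new table beside the on-phase table shows how much the added events change the comparison.

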5.5.9.1. Categorical Safety Variables

Unless specified otherwise, the categorical safety analyses will include both scheduled and unscheduled visits.

Comparisons between treatment groups for all categorical safety measures will be made using Fisher's exact test for SP III in the safety population. Descriptive statistics only will be presented for the analyses with the GMB-treated population.

5.5.9.1.1. Adverse Events

Treatment-emergent AEs are defined as the reported AEs that first occurred or worsened during the post-baseline phase compared with baseline phase. For events occurring on the day of first administration of study drug and on the day of first open-label treatment when applicable, the CRF-collected flag will be used to determine whether the event was pre-treatment versus post-

treatment. For each TEAE, the severity level of the event (mild, moderate, or severe) will be determined by patient or physician opinion. The Medical Dictionary for Regulatory Activities (MedDRA) Lowest Level Term (LLT) will be used in the treatment-emergent computation. For each LLT, the maximum severity at baseline will be used as the baseline severity. If the maximum severity during post-baseline is greater than the maximum baseline severity, the event is considered to be treatment-emergent for the specific post-baseline period. For events with a missing severity during the baseline period, it will be treated as “mild” in severity; for events with a missing severity during the postbaseline period it will be treated as “severe” for TEAE computation. For each patient and TEAE, the maximum severity for the MedDRA level being displayed (PT, High-Level Term [HLT], or SOC) is the maximum postbaseline severity observed from all associated LLTs mapping to that MedDRA level.

For events that are gender-specific, the denominator and computation of the percentage will include only patients from the given gender.

5.5.9.1.1.1. Potential Hypersensitivity Events

Potential hypersensitivity events will be defined using the following terms (standard MedDRA query [SMQ]):

- broad and narrow terms in the Anaphylactic reaction SMQ (20000021)
- broad and narrow terms in the Angioedema SMQ (20000024)
- broad and narrow terms in the Hypersensitivity SMQ (20000214)

A listing of patients having an event identified from these analyses will be medically reviewed to determine if the terms identified represent events likely hypersensitivity in nature. Listings should include information on timing of event relative to latest dose of study drug administration, the event term from this query, other AEs for the patient and timing, any abnormal laboratory findings, concomitant medication, medical history and pre-existing conditions. Only those that are judged medically to be events likely hypersensitivity in nature will be included in the final tables.

The number and percentage of patients with potential and/or likely TEAEs will be summarized by treatment groups using MedDRA PT nested within the SMQ. Events will be ordered by decreasing frequency within the SMQ. The number and percentage of patients with likely hypersensitivity SAEs and AEs resulting in study drug discontinuation will be presented by treatment groups using MedDRA PT, and ordered by decreasing frequency of PT.

The number and percentage of patients with likely hypersensitivity TEAEs by maximum severity will be summarized by treatment groups using MedDRA PT.

The number and percentage of patients with likely hypersensitivity TEAEs by timing will be summarized using MedDRA PT. Events will be ordered by decreasing frequency of PT. Note the timing of the hypersensitivity events is collected through eCRF and categorized into the following four categories:

- immediate - occurs within minutes (<60 minutes) from study drug administration
- acute reaction - occurs from 1 up to 6 hours from study drug administration
- delayed reaction - occurs from >6 hours through 14 days from study drug administration, which will be split into 2 categories: on the same day of injection and after the day of injection
- reaction >14 days

5.5.9.1.1.2. Adverse Events Related to Injection Sites

Adverse events related to injection sites will be defined using terms from the MedDRA HLT Injection site reactions.

The number and percentage of patients with TEAEs related to injection sites, SAEs related to injection sites, and AEs related to injection sites resulting in study drug discontinuation will be summarized using MedDRA PT. Events will be ordered by decreasing frequency of PT term.

The number and percentage of patients with TEAEs related to injection sites by maximum severity will be summarized by treatment groups using MedDRA PT. For each patient and injection site related event, the maximum severity for the MedDRA level being displayed (PT) is the maximum post-baseline severity observed from all associated LLTs mapping to that MedDRA level.

The number and percentage of patients with TEAEs related to injection sites by timing will be summarized using MedDRA PTs ordered by decreasing frequency. Note the timing of AEs related to injection sites is collected through eCRF and categorized into the same categories as for hypersensitivity events.

5.5.9.1.1.3. Upper Respiratory Tract Infections

Upper respiratory tract infections will be defined using all the PTs from the 2 HLTs of “Upper respiratory tract infections” and “Upper respiratory tract infections NEC” as defined in MedDRA.

The number and percentage of patients with TEAEs of upper respiratory tract infections will be summarized by treatment group using MedDRA PTs. Events will be ordered by decreasing frequency in the GMB group.

The number and percentage of patients with TEAEs of upper respiratory tract infections by maximum severity will be summarized by treatment group using MedDRA PTs. For each patient and upper respiratory tract infection event, the maximum severity for the MedDRA level being displayed (PT) is the maximum post-baseline severity observed from all associated LLTs mapping to that MedDRA level.

By-subject listings of treatment-emergent upper respiratory tract infections, and upper respiratory tract infections leading to study drug discontinuation will be provided.

5.5.9.1.2. *Suicide-Related Thoughts and Behaviors*

Postbaseline suicidal ideation, suicidal behavior, and self-injurious behavior without suicidal intent during SP III, based on the C-SSRS, will be summarized by treatment. In particular, for each of the following events, the number and percent of patients with the event will be enumerated by treatment: completed suicide, nonfatal suicide attempt, interrupted attempt, aborted attempt, preparatory acts or behavior, active suicidal ideation with specific plan and intent, active suicidal ideation with some intent to act without specific plan, active suicidal ideation with any methods (no plan) without intent to act, nonspecific active suicidal thoughts, wish to be dead, and self-injurious behavior without suicidal intent. These measures will also be summarized for the GMB-treated population during GMB-treated time and GMB-treated time plus post-treatment time. In addition, the number and percent of patients who experienced at least one of various composite measures during SP III will be presented and compared. These include suicidal behavior (completed suicide, non-fatal suicidal attempts, interrupted attempts, aborted attempts, and preparatory acts or behavior), suicidal ideation (active suicidal ideation with specific plan and intent, active suicidal ideation with some intent to act without specific plan, active suicidal ideation with any methods [no plan] without intent to act, non-specific active suicidal thoughts, and wish to be dead), and suicidal ideation or behavior. These measures will also be summarized for the GMB-treated population during GMB-treated time and GMB-treated time plus post treatment time.

The number and percent of patients who experienced at least one of various comparative measures during treatment will be presented and compared for SP III. These include treatment-emergent suicidal ideation compared to recent history, treatment-emergent serious suicidal ideation compared to recent history, emergence of serious suicidal ideation compared to recent history, improvement in suicidal ideation at endpoint compared to baseline, and emergence of suicidal behavior compared to all prior history. These measures will also be summarized for the GMB-treated population during GMB-treated time and GMB-treated time plus post-treatment time.

Specifically, the following outcomes are C-SSRS categories and have binary responses (yes/no). The categories have been re-ordered from the actual scale to facilitate the definitions of the composite and comparative endpoints, and to enable clarity in the presentation of the results.

Category 1 – Wish to be Dead

Category 2 – Non-specific Active Suicidal Thoughts

Category 3 – Active Suicidal Ideation with Any Methods (Not Plan) without Intent to Act

Category 4 – Active Suicidal Ideation with Some Intent to Act, without Specific Plan

Category 5 – Active Suicidal Ideation with Specific Plan and Intent

Category 6 – Preparatory Acts or Behavior

Category 7 – Aborted Attempt

Category 8 – Interrupted Attempt

Category 9 – Actual Attempt (non-fatal)

Category 10 – Completed Suicide

Self-injurious behavior without suicidal intent is also a C-SSRS outcome (although not suicide-related) and has a binary response (yes/no).

Composite endpoints based on the above categories are defined below.

- Suicidal ideation: A “yes” answer at any time during treatment to any 1 of the 5 suicidal ideation questions (Categories 1-5) on the C-SSRS.
- Suicidal behavior: A “yes” answer at any time during treatment to any 1 of the 5 suicidal behavior questions (Categories 6-10) on the C-SSRS.
- Suicidal ideation or behavior: A “yes” answer at any time during treatment to any 1 of the 10 suicidal ideation and behavior questions (Categories 1-10) on the C-SSRS.

The following outcome is a numerical score derived from the C-SSRS categories. The score is created at each assessment for each patient and is used for determining treatment emergence.

- Suicidal Ideation Score: The maximum suicidal ideation category (1-5 on the C-SSRS) present at the assessment. Assign a score of 0 if no ideation is present.

For SP III, comparative endpoints of interest are defined below. “Treatment emergence” is used for outcomes that include events that first emerge or worsen. “Emergence” is used for outcomes that include events that first emerge.

- Treatment-emergent suicidal ideation compared to recent history:
An increase in the maximum suicidal ideation score during treatment (Visits 3.01 to 9 for SP III) from the maximum suicidal ideation category during the screening and lead-in periods (C-SSRS scales taken at Visits 1 to 3 excluding “lifetime” for SP III).
- Treatment-emergent suicidal ideation compared to all prior history:
An increase in the maximum suicidal ideation score during treatment (Visits 3.01 to 9 for SP III) from the maximum suicidal ideation category prior to treatment (C-SSRS scales taken at Visits 1 to 3 including “lifetime” for SP III).
- Treatment-emergent serious suicidal ideation compared to recent history:
An increase in the maximum suicidal ideation score to 4 or 5 on the C-SSRS during treatment (Visits 3.01 to 9 for SP III) from not having serious suicidal ideation (scores of 0 to 3) during the screening and lead-in periods (C-SSRS scales taken at Visits 1-3 excluding “lifetime” for SP III).
- Treatment-emergent serious suicidal ideation compared to all prior history:
An increase in the maximum suicidal ideation score to 4 or 5 on the C-SSRS during treatment (Visits 3.01 to 9 for SP III) from not having serious suicidal ideation (scores of 0 to 3) prior to treatment (C-SSRS scales taken at Visits 1 to 3 including “lifetime” for SP III).

- Emergence of serious suicidal ideation compared to recent history:
An increase in the maximum suicidal ideation score to 4 or 5 on the C-SSRS during treatment (Visits 3.01 to 9 for SP III) from no suicidal ideation (scores of 0) during the screening and lead-in periods (C-SSRS scales taken at Visits 1 to 3 excluding “lifetime” for SP III). Recent history excludes “lifetime” scores from the baseline C-SSRS scale or Baseline/Screening C-SSRS scale.
- Emergence of serious suicidal ideation compared to all prior history:
An increase in the maximum suicidal ideation score to 4 or 5 on the C-SSRS during treatment (Visits 3.01 to 9 for SP III) from no suicidal ideation (scores of 0) prior to treatment (C-SSRS scales taken at Visits 1 to 3 including “lifetime” for SP III).
- Improvement in suicidal ideation at endpoint compared to baseline:
A decrease in suicidal ideation score at endpoint (the last measurement during treatment; Visits 3.01 to 9 for SP III) from the baseline measurement (the measurement taken just prior to treatment [last non-missing value taken at Visit 2 to Visit 3 for SP III]).
- Emergence of suicidal behavior compared to all prior history:
The occurrence of suicidal behavior (Categories 6 to 10) during treatment (Visits 3.01 to 9 for SP III) from not having suicidal behavior (Categories 6 to 10) prior to treatment (Visits 1 to 3 including “lifetime” for SP III).

Above analyses was only described for SP III, for the analyses including SP IV and SP V, the baseline and postbaseline definition for each of the analyses above is summarized in [Table CGAM.5.5](#).

Table CGAM.5.5. Baseline and Post-Baseline Definition for Treatment-Emergent Suicidal Analyses for GMB-treated Population

Analyses	Study Phase	Baseline	Post-baseline

 Treatment-emergent suicidal ideation compared to recent history Treatment-emergent serious suicidal ideation compared to recent history Emergence of serious suicidal ideation compared to recent history 	III/IV	
Visit 1 to 3 excluding lifetime for GMB-treated patients in SP III;
 
Visit 1 to 9 excluding lifetime for placebo treated patients in SPIII.
	
Visits 3.01 to 22 for GMB-treated patients in SP III;
 
Visits 9.01 to 22 for placebo treated patients in SP III.

	III/IV/V	
Visit 1 to 3 excluding lifetime for GMB-treated patients in SP III;
 
Visit 1 to 9 excluding lifetime for placebo treated patients in SPIII.
	
Visits 3.01 to 24 for GMB-treated patients in SP III;
 
Visits 9.01 to 24 for placebo treated patients in SP III.

 Treatment-emergent suicidal ideation compared to all prior history Treatment-emergent serious suicidal ideation compared to all prior history Emergence of serious suicidal ideation compared to all prior history Emergence of suicidal behavior compared to all prior history 	III/IV	
Visit 1 to 3 including lifetime for GMB-treated patients in SP III;
 
Visit 1 to 9 including lifetime for placebo treated patients in SPIII.
	
Visits 3.01 to 22 for GMB-treated patients in SP III;
 
Visits 9.01 to 22 for placebo treated patients in SP III.

	III/IV/V	
Visit 1 to 3 including lifetime for GMB-treated patients in SP III;
 
Visit 1 to 9 including lifetime for placebo treated patients in SPIII.
	
Visits 3.01 to 24 for GMB-treated patients in SP III;
 
Visits 9.01 to 24 for placebo treated patients in SP III.

Improvement in suicidal ideation at endpoint compared to baseline	III/IV	
Last non-missing measure prior to or at visit 3 for GMB-treated patients in SP III;
 
Last non-missing measure prior to or at visit 9 for GMB-treated patients in SP III.
	
Last value during Visits 3.01 to 22 for GMB-treated patients in SP III;
 
Last value during Visits 9.01 to 22 for GMB-treated patients in SP III.

Baseline and Post-Baseline Definition for Treatment Emergent Suicidal Analyses for GMB-treated Population

Analyses	Study Phase	Baseline	Post-baseline
	III/IV/V	Last non-missing measure prior to or at visit 3 for GMB-treated patients in SP III; Last non-missing measure prior to or at visit 9 for GMB-treated patients in SP III.	Last value during Visits 3.01 to 24 for GMB-treated patients in SP III; Last value during Visits 9.01 to 24 for GMB-treated patients in SP III.

Abbreviations: GMB = galcanezumab; SP = study phase.

Patients who discontinued from the study with no postbaseline C-SSRS value will be considered unevaluable for analyses of suicide-related events. Only evaluable patients will be considered in the analyses. Fisher's exact test will be used for treatment comparisons in SP III.

5.5.9.1.3. **Vital Signs and Weight**

Vital signs collected during the study include systolic and DBP, pulse, and temperature. Blood pressure and pulse measurements will be taken when the patient is in a sitting position. Three measurements of sitting BP and pulse will be collected at approximately 30 to 60 second intervals at every visit and the 3 sitting BP measurements and 3 pulse values will be averaged and used as the value for that visit.

Table CGAM.5.6 displays the criteria used to define treatment-emergent, potentially clinically significant changes and sustained elevation in vital signs and weight. The last column of the table displays the patient population for each analysis based on baseline categories. The number and percent of patients meeting these criteria will be summarized. Treatment group comparisons will be performed using Fisher's exact test for SP III.

The criteria to identify patients with treatment-emergent abnormal changes generally consist of 2 parts, an absolute threshold and a change from baseline amount.

- The absolute threshold in the criteria is based on 1) minimum postbaseline when the direction is low; 2) maximum postbaseline when the direction is high.
- The change from baseline amount in the criteria is 1) decrease from baseline (defined below and in Table CGAM.5.3) to minimum postbaseline when the direction is low; 2) increase from baseline (defined below and in Table CGAM.5.3) to maximum postbaseline when the direction is high.

The baseline for systolic blood pressure (SBP), DBP, and pulse is defined as the last non-missing baseline value during the baseline period (See Table CGAM.5.3). To be exact,

